I understand that all documentation provided to me by Rhythm Pharmaceuticals, Inc. (Rhythm; the sponsor) or its designated representative(s) concerning this trial that has not been published previously will be kept in the strictest confidence. This documentation includes the trial protocol, Investigator Brochure (IB), case report forms, and other scientific data.

This trial will not commence without the prior written approval of a properly constituted Institutional Review Board/Independent Ethics Committee. No changes will be made to the trial protocol without the prior written approval of the sponsor and the Institutional Review Board/Independent Ethics Committee, except where necessary to eliminate an immediate hazard to the patient.

I have read, understood, and agree to abide by all the conditions and instructions contained in this protocol.

Investigator Name

Investigator Signature

Date

Investigational site or name of institution and location (printed)

	CLINICAL INIAL STINOI SIS
Sponsor	Rhythm Pharmaceuticals, Inc.
Investigational Drug Product	Setmelanotide (RM-493)
Protocol Number	RM-493-022
Protocol Title	Long-Term Extension Trial of Setmelanotide (RM-493) for Patients Who Have Completed a Trial of Setmelanotide for the Treatment of Obesity Associated with Genetic Defects Upstream of the MC4 Receptor in the Leptin-Melanocortin Pathway This extension trial applies to patients with rare genetic, syndromic, or acquired diseases of obesity and obesity potentially related to other abnormalities in the MC4 receptor pathway.
Clinical Phase/Trial Type	Open-label active treatment extension trial (Phase 2/3)
Treatment Indication	Treatment of obesity associated with genetic defects upstream of the MC4 receptor (MC4R) in the leptin-melanocortin pathway and with obesity related to other abnormalities in the MC4R pathway.
Objective(s)	Primary To characterize safety and tolerability of setmelanotide in patients who have completed a previous trial on treatment with setmelanotide for obesity associated with genetic defects upstream of the MC4R in the leptin-melanocortin pathway and with obesity related to other abnormalities in the MC4R pathway.
Trial Design	This is a long-term (treatment for up to 7 years) extension trial designed to evaluate the safety and tolerability of continued

CLINICAL TRIAL SYNOPSIS

	setmelanotide treatment in patients who have completed a previous clinical trial on treatment with setmelanotide for rare genetic, syndromic, or acquired diseases of obesity upstream of the MC4R in the melanocortin-leptin pathway and other abnormalities of the MC4R pathway. Patients who complete treatment in a previous trial (index trial) of setmelanotide and wish to continue with setmelanotide treatment will be considered for eligibility to enter this extension trial. Patients (or their legal guardians) will provide informed consent/assent to participate in this extension trial, and eligibility will be confirmed prior to completion of their index trial.
	Visit 1 of this trial will coincide with the final visit of the index trial; see Table 1 for details. Generally, there should be no gaps in treatment during the transition from the index trial to this extension trial. A gap in treatment between the index trial and extension trial may be allowed for individual patients, with approval by the sponsor. Patients will begin this extension trial on the same dose of setmelanotide that they were taking when they completed their index trial. Patients who received double-blind study drug in a placebo-controlled index trial will start open-label setmelanotide in this trial, with the starting dose from the index trial. The dose titration should follow the scheme in the index trial and in consultation with the sponsor.
	Patients will be evaluated approximately every 3 months at the trial site for adverse events (AEs), concomitant medications, height (in children), Additional tests will be completed at longer trial visit intervals.
Trial Population	Male and female patients who have completed all critical trial evaluations in a previous setmelanotide trial and would benefit from continued setmelanotide treatment.
Number of Patients & Trial Centers	It is anticipated that any patient receiving active therapy from a setmelanotide clinical trial and experiencing improvements in weight-related parameters could be a candidate for enrollment in this extension trial. Based on the number of patients currently enrolled or planned for enrolment in current or future setmelanotide clinical trials, it is anticipated that up to 500 patients may be enrolled in this trial; however, expansion in enrollment may occur if additional patients with obesity due to monogenic, syndromic or acquired disorders affecting the MC4R pathway are enrolled in Phase 2 or Phase 3 clinical trials evaluating setmelanotide. It is anticipated that up to 100 centers located worldwide will participate in this trial. In the event additional patients are to be enrolled, additional sites may be added, as necessary.

Inclusion Criteria	 Patients aged 2 or older (or aged >2 years as per local regulations; only patients aged 12 years or older may be enrolled in the trial in Greece; only patients 6 years or older may be enrolled in the trial in Germany) who have completed participation in a previous setmelanotide clinical trial.
	2. If patient received setmelanotide on an open-label basis in a previous setmelanotide clinical trial, patient demonstrated adequate safety and meaningful clinical benefit (efficacy) in the previous setmelanotide trial. Meaningful clinical benefit is defined as follows:
	• Patients 18 years of age or younger that have completed participation on active drug and demonstrated adequate safety and at least 3% BMI reduction or reduction in BMI Z-score of 0.2 compared to baseline.
	• Patients over 18 years of age should show reduction of 3% BMI compared to baseline.
	If the patient participated on a double-blind basis in the previous placebo-controlled clinical trial, patient tolerated blinded study drug.
	3. Patient and/or parent or guardian is able to communicate well with the investigator, to understand and comply with the requirements of the trial, and to understand and sign the written informed consent/assent. The patient must consent/assent to participate in the trial.
	4. Patient must meet one of the following requirements regarding contraception:
	• If a female of childbearing potential, defined as fertile, following menarche and until becoming post- menopausal unless permanently sterile (hysterectomy, bilateral salpingectomy, or bilateral oophorectomy), must use a highly effective form of contraception as outlined in Section 6.2.1.
	• If a female of non-childbearing potential, defined as permanently sterile (status post hysterectomy, bilateral oophorectomy, or bilateral salpingectomy) or post- menopausal for at least 12 months (and confirmed with a screening follicle-stimulating hormone (FSH) level in

		the post-menopausal laboratory range), contraception is not required during the trial.
		 Younger female patients who have not reached menarche upon trial entry will be assessed for Tanner staging and at first menarche will be required to comply with contraception requirements and pregnancy testing as outlined in the protocol.
		• If a male with female partner(s) of childbearing potential, must agree to a double barrier method if they become sexually active during the trial. Furthermore, male patients must not donate sperm during and for 90 days following their participation in the trial.
Exclusion Criteria	1.	Pregnant and/or breastfeeding women.
	2.	Significant dermatologic findings relating to melanoma or pre- melanoma skin lesions (excluding non-invasive basal or squamous cell lesion), determined as part of a screening comprehensive skin evaluation performed by a qualified dermatologist. Any concerning lesions identified during the screening period will be biopsied and results known to be benign prior to enrollment. If the pre-treatment biopsy results are of concern, the patient may need to be excluded from the trial.
	3.	Patient is, in the opinion of the investigator, not suitable to participate in the trial.
	4.	Current, clinically significant disease, if severe enough to interfere with the trial and/or would confound the results. Any such patients should be discussed with the sponsor prior to enrollment in the trial.
	5.	Diagnosis of schizophrenia, bipolar disorder or other psychiatric disorder that the investigator believes will interfere significantly with trial compliance.
	6.	A Patient Health Questionnaire-9 (PHQ-9) score of ≥ 15 .
	7.	Severity Rating Scale (C-SSRS). Any lifetime history of a suicide attempt, or any suicidal behavior since the last visit in the index trial.
		Note: Patients who are unable to complete the C-SSRS due to significant neurocognitive defects may be enrolled in the trial, as long as in the opinion of the investigator there are no clinical signs or symptoms of suicidal behavior.
	8.	History of significant liver disease or liver injury, or a current liver assessment due to abnormal liver tests (as indicated by abnormal liver function tests, alanine transaminase [ALT],

	 aspartate transaminase [AST], alkaline phosphatase, or serum bilirubin >1.5× the upper limit of normal [ULN] for any of these tests) for an etiology other than non-alcoholic fatty liver disease (NAFLD). Thus, any underlying etiology besides NAFLD, including diagnosed non-alcoholic steatohepatitis (NASH), other causes of hepatitis, or history of hepatic cirrhosis is exclusionary, but the presence of NAFLD is not exclusionary. 9. Severe renal dysfunction defined by a glomerular filtration rate (GFR) <30 mL/min/1.73 m² in patients <12 years of age or end stage renal disease (GFR <15 mL min/1.73 m² (see Appendix 11.4 for GFR calculation). 10. History or close family history (parents or siblings) of skin cancer or melanoma (not including non-invasive/infiltrative basal or squamous cell lesion), or patient history of ocular-cutaneous albinism.
Trial Procedures	The safety and tolerability of setmelanotide will be assessed by the frequency and severity of AEs as well as changes in physical examinations, electrocardiograms (ECGs), vital signs, laboratory evaluations, and injection site reactions.
Study Drug and Administration	All study drugs are for investigational use only and are to be used only within the context of this protocol. Setmelanotide will be supplied by the sponsor. Setmelanotide will be administered as a subcutaneous (SC) injection once daily. Setmelanotide doses and titration steps will follow the index trial scheme (Section 5.2).
Statistical Considerations	A detailed Statistical Analysis Plan will describe all analyses for this extension trial.A by-patient AE data listing including onset and resolution dates, verbatim term, preferred term, treatment, severity, relationship to treatment, action taken, and outcome will be provided.

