4.2.1. Inclusion Criteria

- 1. Patients aged 2 or older (or aged >2 years as per local regulations; ; only patients aged 12 years or older may be enrolled in the trial in Greece; only patients 6 years or older may be enrolled in the trial in Germany) who have completed participation in a previous setmelanotide clinical trial.
- 2. If patient received setmelanotide on an open-label basis in a previous setmelanotide clinical trial, patient demonstrated adequate safety and meaningful clinical benefit (efficacy) in the previous setmelanotide trial. Meaningful clinical benefit is defined as follows:
 - Patients 18 years of age or younger that have completed participation on active drug and demonstrated adequate safety and at least 3% BMI reduction or reduction in BMI Z-score of 0.2 compared to baseline.
 - Patients over 18 years of age should show reduction of 3% BMI compared to baseline.

If the patient participated in a double-blind basis in the previous placebo-controlled clinical trial, patient tolerated blinded study drug.

- 3. Patient and/or parent or guardian is able to communicate well with the investigator, to understand and comply with the requirements of the trial, and to understand and sign the written informed consent/assent. The patient must consent/assent to participate in the trial.
- 4. Patient must meet one of the following requirements regarding contraception:
 - If a female of childbearing potential, defined as fertile, following menarche and until becoming post-menopausal unless permanently sterile (hysterectomy, bilateral salpingectomy, or bilateral oophorectomy), must use a highly effective form of contraception as outlined in Section 6.2.1.
 - If a female of non-childbearing potential, defined as permanently sterile (status post hysterectomy, bilateral oophorectomy, or bilateral salpingectomy) or postmenopausal for at least 12 months (and confirmed with a screening folliclestimulating hormone (FSH) level in the post-menopausal laboratory range), contraception is not required during the trial.
 - Younger female patients who have not reached menarche upon trial entry will be assessed for Tanner staging and at first menarche will be required to comply with contraception requirements and pregnancy testing as outlined in the protocol.

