5.2. Study Drug Dose and Administration and Dose Adjustments

Study Drug Dose at Trial Entry: Patients who received setmelanotide on an open-label basis in the index trial will begin this extension trial on the same dose of setmelanotide they were taking when they completed their index trial, unless tolerability or safety reasons justify a dose decrease. Patients who received double-blind study drug in a placebo-controlled index trial will start open-label setmelanotide in this trial with the starting dose from the index trial. The dose titration should follow the scheme in the index trial and in consultation with the sponsor.

Study Drug Administration: Trial patients will receive open-label setmelanotide by SC injection once daily (administered in the morning). Patients and/or their caregivers (including home health practitioners) will be responsible for all procedures associated with study drug administration at all times, i.e., drawing up, and self-administering the study drug once daily. Patients should be

instructed to rotate injection sites as per the dosing instructions and to avoid tight fitting clothing near the injection site to potentially reduce any injection site reactions.

Study drug is administered by patients/caregivers beginning the morning of Day 1 and for the duration of dosing. (If the index study drug is administered on the last day of the index trial/Day 1 of the current trial, then study drug administration in the current trial will begin on Day 2.) Patients/caregivers will draw up and self-administer/administer the drug once on a daily basis in the morning. On days with clinic visits, the patients/caregivers will administer the drug in the clinic in the presence of the clinical staff to ensure proper technique. Patients/caregivers will return all used vials to the clinic when they visit (the number recorded) and both clinic administration of study drug, as well as outpatient study drug administration will be recorded in a trial diary.

Study Drug Administration in Patients with Severe Renal Impairment

In Patients ≥ 12 years of age with severe renal impairment (eGFR 15 to 29 mL min/1.73 m²), the starting dose of setmelanotide is 0.5 mg (0.5 mL) injected subcutaneously QD for 2 weeks. The dose may be increased by 0.5 mg QD every 2 weeks, if tolerated, to a maximum of 1.5 mg QD. If the starting dose is not tolerated, treatment should be discontinued.

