1.3.2. Stopping Rules and Unblinding

This study is open label so there is no blinding. All blinded index trials have been completed and are unblinded for analysis of RM-493-022.

A specific gene cohort or the whole trial may be terminated, if in the opinion of the investigator (at a participating site) or Rhythm (for the whole study), there is sufficiently reasonable cause. The terminating party will provide written notification documenting the reason for termination to either the investigator or Rhythm. Circumstances that may warrant termination include, but are not limited to:

- Determination of unexpected, significant, or unacceptable risk to subjects
- Failure to enter subjects at an acceptable rate
- Insufficient adherence to protocol requirements
- Insufficient complete and/or evaluable data
- Plans to modify, suspend or discontinue the development of the study drug
- Lack of clinical efficacy
- 1.3.3. Randomization Methodology

As this is a single arm, open-label study, there will be no randomization in this trial.

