2. SUBJECT POPULATIONS

2.1. **Population Definitions**

• Safety Analysis Population (SAS) – The SAS includes all subjects who received at least one dose of treatment in RM-493-022. The safety population will be used for all analyses.

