3.5. Methods of Pooling Data

For safety-related analyses, data will be pooled across index studies and rare genetic disorders of obesity and summarized together. For non-safety-related analyses, data will be pooled by rare genetic disorder of obesity within study, as applicable, and data will therefore be summarized by index study.

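### Pooled AE incidence mixes open-label continuers with double-blind entrants who start or restart setmelanotide, so it cannot be read as the rate under continued treatment

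*Protocol*

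**What the plan says.** The primary objective (protocol synopsis and 2.1.1) is "To characterize safety and tolerability of setmelanotide in patients who have completed a previous trial on treatment with setmelanotide". The objective does not itself mention continuation. That comes from the synopsis design text, which calls this an "extension trial designed to evaluate the safety and tolerability of continued" treatment, and from protocol 8.2, which hypothesises that the drug goes on being safe and well tolerated.

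Protocol 4.2.1, criterion 2, has two entry routes:

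- Open-label index patients enter if the "patient demonstrated adequate safety and meaningful clinical benefit (efficacy) in the previous setmelanotide trial".
- For the others: "If the patient participated in a double-blind basis in the previous placebo-controlled clinical trial, patient tolerated blinded study drug". No benefit test applies, and the placebo arm is not excluded.

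Protocol 5.2 keeps open-label patients on their last index dose unless tolerability or safety justifies a decrease. For the other route it says: "Patients who received double-blind study drug in a placebo-controlled index trial will start open-label setmelanotide in this trial", at the index starting dose and with the index titration scheme.

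SAP 2.1 has a single analysis set: "The SAS includes all subjects who received at least one dose of treatment in RM-493-022". SAP 3.5 states: "For safety-related analyses, data will be pooled across index studies and rare genetic disorders of obesity and summarized together". SAP 3.8 defines no subpopulations. In SAP 4.5.2 the AE listings are sorted by index study. SAP 1.3.2 adds: "All blinded index trials have been completed and are unblinded for analysis of RM-493-022".

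**The concern.** AE frequency and severity form the leading part of the primary endpoint. Three entry states can feed the same incidence table: uninterrupted continuers selected for tolerating the drug, double-blind active patients who go back to the starting dose, and double-blind placebo patients who would be taking setmelanotide for the first time. Their AE rates should differ, for reasons found in the documents:

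- The treatment-emergent clock starts at the extension Day 1 dose for everyone (footnote 22 of the schedule of assessments).
- AEs ongoing at the final index visit are logged as pre-existing (protocol section 7). An event present at baseline counts as treatment-emergent only if it worsens or is later judged drug-related (protocol 8.4).
- Skin hyperpigmentation, a listed common reaction (protocol 7.3), was reported in the first 7 to 14 days of treatment (protocol Appendix 11.2).

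The same reaction would therefore be a new event in a first-time user, but usually not in a continuer who developed it during the index trial. A statement about long-term tolerability drawn from the pooled table could be too high for continuers and too low for starters, and the reader could not tell by how much.

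**Working it through.** The plan states no AE rate, sample size or power, so there is no figure of its own to reproduce.

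**Step 1. Does any planned output separate the groups?**

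| Output | Breakdown given | Separates exposure at entry? |
|---|---|---|
| Safety summaries (SAP 3.5) | Pooled | No |
| AE listings (SAP 4.5.2) | Sorted by index study | No, index arm not shown |
| Disposition, including reasons for discontinuation (SAP 4.1) | Index study and overall | No, index arm not shown |
| Exposure (SAP 4.5.1) | Extension only, and index plus extension | No, a duration and not a grouping |
| Separate analyses in protocol 3.1 and 8.3 | Disease population | No |

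The AE summary sentence in SAP 4.5.2 breaks off in the public text, so the full list of AE tables cannot be seen. The finding rests on the general rules in SAP 3.5 and 3.8.

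**Step 2. How many patients could be affected?** SAP Table 1-1 gives 9 + 13 + 119 + 12 + 38 + 14 + 1 = 206. It does not say which studies were placebo-controlled. The number of setmelanotide-naive entrants, n, is not given. I let n run from 0 to 103 (0% to 50%) as an assumed range. The upper end is an outer limit and not an estimate: the six studies other than 014 contribute only 206 − 119 = 87 patients.

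**Step 3. Illustration.** Let s = n/206, and let the continuing and first-time rates be r_c and r_f (both assumed).

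Pooled rate = s × r_f + (1 − s) × r_c, so the shift from the continuing rate = s × (r_f − r_c).

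| n (s) | Pooled at r_c 20%, r_f 60% | Shift, 20%/60% | Shift, 10%/60% | Shift, 30%/50% |
|---|---|---|---|---|
| 0 (0%) | 20.0% | 0.0 | 0.0 | 0.0 |
| 10 (4.9%) | 21.9% | 1.9 | 2.4 | 1.0 |
| 21 (10.2%) | 24.1% | 4.1 | 5.1 | 2.0 |
| 41 (19.9%) | 28.0% | 8.0 | 10.0 | 4.0 |
| 103 (50.0%) | 40.0% | 20.0 | 25.0 | 10.0 |

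Shifts are in percentage points. For n = 41 at 20%/60%: 41 × 0.60 = 24.6 and 165 × 0.20 = 33.0 expected patients with the event, 57.6 in all. Then 57.6/206 = 28.0%, and first-time users supply 24.6/57.6 = 43% of the patients with the event while being 20% of the population.

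The model has two groups only. Double-blind active patients who re-titrate would be a third, with a rate that the documents give no basis to assume.

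**The case against.** The strongest objection is that nothing shows a naive patient was ever enrolled. Protocol 4.2.1 and 5.2 permit it, but Table 1-1 labels no index study as placebo-controlled, and SAP 1.3.2 does not describe the arms of the blinded trials or any open-label phase within them. Two places read as if every entrant had already had active drug: SAP 3.4 sets index baseline before the first active dose in the index study, and the synopsis entry on number of patients describes candidates as on active therapy and improving. Protocol 4.1, however, describes as a candidate any participant in a setmelanotide trial. This objection stands on size: the distortion may be zero. It does not dispose of the point, because without a count or a split the reader cannot tell zero from large.

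A reader might infer that the pooled rate describes neither group. The documents do not support that. At a naive share near 5%, the pooled rate stays within about 1 to 2.4 points of the continuing rate under the assumed rates, although it still hides the rate in starters.

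A reader might also infer that the primary result should be limited to patients with prior exposure. That would drop dosed patients from the set that SAP 2.1 uses throughout, and would again mix re-titrating double-blind active patients with uninterrupted continuers.

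Finally, SAP 3.7 makes interpretation descriptive, and no test or threshold uses the pooled rate. That limits the consequence to how the results are read.

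**Conclusion.** The point holds in a limited form. The entry rules allow patients in different states of exposure, and the SAP's general rules pool their AEs without a split, so the pooled incidence cannot be read as the rate under continued treatment. How far it departs from that rate is unknown: nil if no naive or re-titrating patients entered; under the assumed rates, 1.0 to 2.4 points with 10 naive patients and 4.0 to 10.0 points with 41. All rates and counts of naive patients here are assumptions; only the 206 comes from the plan. The change is a cheap improvement to reporting and leaves the primary analysis population as it is.

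**What to change.** Keep the all-dosed safety population as the primary summary and make these additions:

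1. SAP 4.1: state the number of entrants by exposure at entry, as open-label continuers, double-blind active, and double-blind placebo (setmelanotide-naive).
2. SAP 4.5.2, and AE-related discontinuation in SAP 4.1: add a column for each group beside the overall column. Base statements about continued treatment on the open-label continuer column.
3. Footnote these tables to say that open-label entrants were selected for adequate safety in the index trial, subject to the documented case-by-case exceptions that protocol 4.2 allows.
4. If no naive or re-titrating patients were enrolled, one sentence saying so replaces all of the above.

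The cost is SAP wording and one grouping variable from index treatment codes that SAP 1.3.2 says are already unblinded. The downside is wider tables and small counts in some columns.
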